#### • Partial Remission (PR)

For subjects to be classified as being in PR, they must have bone marrow regenerating normal hematopoietic cells with evidence of peripheral recovery with no (or only a few

regenerating) circulating blasts and with a decrease of at least 50% in the percentage of blasts in the bone marrow aspirate with the total marrow blasts between 5% and 25%.

### • Morphologic leukemia-free state (MLFS):

Bone marrow: ≤5% myeloblasts

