#### 4.4.2 Endpoints & Assessment Methods

Objective Overall Response Rate (ORR) for subjects with AML include CR, CRi, PR and morphologic leukemia-free state [22] with or without cytogenetic response and hematologic improvements. The responses are defined as below:

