### Complete Remission (CR)

For subjects to be classified as being in CR, they must have bone marrow regenerating normal hematopoietic cells and achieve a morphologic leukemia-free state and must have an ANC >  $1 \times 10^9$ /L and platelet count  $\ge 100 \times 10^9$ /L, and normal marrow differential with < 5% blasts, and subjects will be red blood cell (RBC) and platelet transfusion independent (defined as 4 weeks without RBC transfusion and 1 week without platelet transfusion). There should be no evidence of extramedullary leukemia.

Complete Remission with Incomplete Hematological Recovery (CRi)
 For subjects to be classified as being in CRi, they must fulfill the criteria for CR except for incomplete hematological recovery with residual neutropenia (ANC ≤ 1 × 10^9/L) with or without thrombocytopenia (platelet count < 100 × 10^9/L). In addition, subjects do not need to be RBC or platelet transfusion independent (modification to Cheson criteria).

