### • Recurrence of Disease (RD)

Relapse after CR is defined as a reappearance of leukemic blasts in the peripheral blood or  $\geq 5\%$  blasts in the bone marrow aspirate not attributable to any other cause or reappearance or new appearance of extramedullary leukemia. Relapse after PR is similarly defined with reappearance of significant numbers of peripheral blasts and an increase in the percentage of blasts in the bone marrow aspirate to > 25% not attributable to any other cause or reappearance or new appearance of extramedullary leukemia.

Best Response measurement: Response will be measured and defined for primary endpoints as the best response achieved during the first 3 cycles of therapy, or at time off study, for those subjects discontinuing treatment before the completion of 3 cycles of therapy. Best response is defined to be the best-measured response (ORR=CR+CRp+PR+MLFS) post-treatment up to that time. Best response will also be evaluated for the full treatment period using all assessments up to and including treatment discontinuation.

**Duration of Response**: length of time from the first objective evidence of response to the first objective evidence of disease progression.

**Progression-Free Survival**: length of time (up to 5 years) from the date of first treatment to the first objective evidence of disease progression or death, whichever is earlier.

**Overall Survival**: length of time from the date of first administration of study drug to the date of death from any cause.

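### MLFS counts as a response on marrow blasts of 5% or less alone, so ORR can credit a subject who still has leukemia or whose marrow was already low at screening

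*Combined protocol and SAP*

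**What the plan says.** Section 4.4.2 (Endpoints & Assessment Methods) says that ORR is to "include CR, CRi, PR and morphologic leukemia-free state [22] with or without cytogenetic response and hematologic improvements", and then "The responses are defined as below". The paragraph on best response repeats the composition: "Best response is defined to be the best-measured response (ORR=CR+CRp+PR+MLFS) post-treatment up to that time".

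The MLFS entry consists of one line, "Bone marrow: ≤5% myeloblasts".

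The neighbouring entries are stricter or differ at the boundary:

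- CR requires MLFS and, in addition, "normal marrow differential with < 5% blasts", count recovery and transfusion independence. It adds: "There should be no evidence of extramedullary leukemia".
- PR requires at least a 50% fall in marrow blasts, no circulating blasts beyond a few regenerating ones, and "total marrow blasts between 5% and 25" per cent.
- Relapse after CR is "reappearance of leukemic blasts in the peripheral blood or" marrow blasts at or above 5%, or extramedullary leukemia that reappears or newly appears.

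Section 4.4.1 reports ORR and each response category with exact 95% confidence intervals, on the Full Analysis Set. The inclusion criteria in Section 5.1 set no minimum marrow blast percentage.

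**The concern.** A category called leukemia-free is easier to reach than partial remission. PR demands a halving of marrow blasts and limits what may circulate; MLFS demands neither. Elsewhere the protocol treats the omitted findings as leukemia. Sections 4.1.10 and 4.1.11 list new extramedullary leukemia as clinical evidence of progressive disease. Section 4.1.9.1 groups persistent peripheral blasts with a marrow above 5% blasts.

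At stake is the credibility of the response rate. ORR is a secondary objective, and response data are among the inputs to the RP2D assessment in Section 4.1.7. In a small single-arm study, one or two subjects credited without a real response visibly change the reported rate.

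**Working it through.** The plan gives no response-rate figure to reproduce, so the check applies the written rules to test cases and then works out what one subject is worth.

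**Rules applied, all from Section 4.4.2.** MLFS: marrow ≤5%. CR marrow: <5%. PR marrow: 5% to 25%, taken as inclusive, with a fall of at least 50%. Relapse-after-CR findings: circulating leukemic blasts, or marrow ≥5%, or extramedullary leukemia.

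| Case | Marrow, screening to visit | Circulating blasts | Extramedullary | MLFS as written | PR marrow rule | Finding that defines relapse after CR | MLFS after the fix |
|---|---|---|---|---|---|---|---|
| a | 40% to 5% | no | no | yes | yes | yes | no |
| b | 8% to 5% | no | no | yes | no | yes | no |
| c | 40% to 4% | yes | no | yes | no | yes | no |
| d | 40% to 4% | no | yes | yes | no | yes | no |
| e | 4% to 4% | yes | no | yes | no | yes | no |
| f | 40% to 4% | no | no | yes | no | no | yes |

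The fall in case b is (8 − 5)/8 = 37.5%, short of the 50% that PR needs. In case a it is (40 − 5)/40 = 87.5%.

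**Which cases can move ORR.** Cases b to e can, in a subject never in CR or PR, because MLFS alone then makes the subject a responder. Case e shows no change in marrow at all. Where case a meets the remaining PR conditions (regenerating marrow, peripheral recovery), it is in ORR under either label, so the overlap shifts the PR and MLFS proportions and leaves ORR alone. Case f shows that a clean MLFS survives the fix.

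**Value of one subject.** The change in ORR is 1/n.

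- Whole study, up to 48 subjects (Section 4.1.4): 1/48 = 2.1 points.
- Expansion phase, 12 new plus 6 carried over = 18 (Section 4.1.5): 1/18 = 5.6 points.

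Exact (Clopper-Pearson) 95% limits are the 0.025 quantile of Beta(x, n − x + 1) and the 0.975 quantile of Beta(x + 1, n − x), with a lower limit of 0 when x = 0. The responder counts below are assumed for illustration.

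| n | Without the subject | With the subject |
|---|---|---|
| 18 | 0/18 = 0% (0 to 18.5) | 1/18 = 5.6% (0.1 to 27.3) |
| 18 | 3/18 = 16.7% (3.6 to 41.4) | 4/18 = 22.2% (6.4 to 47.6) |
| 48 | 0/48 = 0% (0 to 7.4) | 1/48 = 2.1% (0.05 to 11.1) |

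**The case against.** The strongest defence is that the MLFS line is shorthand. Section 4.4.2 attaches a citation to MLFS, and the CRi entry flags where it departs from the cited criteria, which suggests that the source applies elsewhere. A detailed SAP is promised before database lock and could fill the gap. MLFS is also tabulated separately and all data are listed by subject, so a reader could see an ORR driven by MLFS.

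Part of this stands: the separate tabulation limits the harm, and later clarification cannot be ruled out. But the text says that the definitions below it govern. CR also adds the stricter blast threshold and the absence of extramedullary disease on top of MLFS, which would be redundant if MLFS already carried them. Listings let a reader notice a problem; they do not change who is counted.

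Four stronger readings are tempting, and the documents do not support them:

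- **That ORR is inflated by subjects who are formally in relapse or in PR.** The relapse rules apply only after CR or PR. Such a subject is already in ORR through the earlier response, because best response keeps the best result up to that time. A subject in PR is likewise already counted. In subjects never in CR or PR, the findings resemble relapse but are not relapse under the plan.
- **That duration of response becomes zero or undefined.** It ends at the first objective evidence of progression, not at the relapse criteria, and a finding that merely persists at the response visit is not shown to be progression.
- **That the bias is far larger within a dose cohort.** Section 4.4.1 specifies no ORR by cohort.
- **That exactly 5% must be common because blast counts are rounded.** The documents do not say how counts are reported.

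**Conclusion.** The concern holds as a fault in the written response definition. Followed as stated, it can credit a response to a subject with marrow blasts of 5% or less who has circulating leukemic blasts or extramedullary leukemia, who sits at exactly 5% without a 50% fall, or who already had a low marrow count at screening. Because the missing conditions could only remove responders, any error runs upward.

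The size is 2.1 points per affected subject on a denominator of 48, or 5.6 points on 18. Section 4.4.1 names only the Full Analysis Set, so the 18-subject figure assumes that ORR is also reported for the expansion phase, and 48 is the enrolment ceiling. The number of affected subjects is unknown and may be zero. The PR overlap at exactly 5% depends on reading the PR range as inclusive and affects category proportions only. DLT and MTD conclusions do not depend on ORR.

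**What to change.** In Section 4.4.2, or in the SAP before database lock, state that for response classification MLFS means marrow blasts below 5%, no circulating leukemic blasts and no extramedullary leukemia, in a subject who did not already meet those conditions at screening. This brings MLFS into line with the CR and relapse cutoffs.

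Two drafting points follow. First, CR requires MLFS, so the screening condition should govern only whether MLFS is credited as a response; otherwise it could disqualify a genuine CR. Second, state whether the PR range includes 5%, so that a marrow at exactly that value has one place to go.

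No new procedure is needed. The flowcharts in Section 4.2 already schedule marrow, blood count with differential and physical examination at screening and at the ends of Cycles 1 and 3. The cost is one or two sentences and possibly a slightly lower ORR.

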#### Hematologic Improvement (HI):

Hematologic response must be described by the number of positively affected cell lines.

- Erythroid response (E) (pretreatment Hgb <11 g/dL)

- Hgb increase by ≥1.5 g/dL
- Platelet response (P) (pretreatment platelets <100 x10^9/L)
- Absolute increase of  $\ge 30 \times 10^9$ /L for subjects starting with  $> 20 \times 10^9$ /L platelets
- $\circ$  Increase from < 20 x 10^9/L to > 20 x 10^9/L and by at least 100%
- Neutrophil response (N) (pretreatment ANC <1.0 x10^9/L)
- o At least 100% increase and an absolute increase > 0.5 x 10^9/L
- Blast response (B)≥50% reduction in peripheral blood or bone marrow blasts but still >5%

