### 4.4 Clinical Efficacy

### 4.4.1 Subject Evaluation & Statistics

The FAS will be the basis for the evaluation of clinical efficacy.

Disease assessment will be performed at the end of Cycles 1, 3, and thereafter every 2-3 cycles at the discretion of the treating physician. While the bone marrow aspirate/biopsy will be performed as clinically indicated, testing will occur at least once every 3 cycles.

Descriptive statistics will be provided for continuous variables and frequency tables will be used to summarize categorical variables. The Overall Response Rate and the proportions of subjects who experienced CR, Cri, PR, MLFS (morphologic leukemia-free state), hematologic improvements, Recurrence of Disease (RD) and Best Response measurement along with the corresponding exact 95% confidence intervals will be displayed.

Kaplan-Meier method will be used to estimate the duration of response, progression-free survival and overall survival. These time to event variables will be summarized using the 25th percentile, Median, and 75th percentile as well as the minimum and maximum time to event, calculated by Kaplan-Meier method, and will be displayed graphically.

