- 7. Have been informed of other treatment options and is not a candidate for standard treatment options or stem cell transplant at the time of enrollment.
- 8. Age  $\geq$ 18 years.
- 9. In the absence of rapidly progressing disease, the interval from prior treatment to time of initiation of IACS-010759 administration will be at least 2 weeks or 5 half-lives (whichever is shorter) for cytotoxic/noncytotoxic agents and biological/immune-based therapies, including investigational agents. The half-life for the therapy in question will be based on published pharmacokinetic literature (abstracts, manuscripts, investigator brochures, or drug-administration manuals) and will be documented in the protocol eligibility document. The use of chemotherapeutic or anti-leukemic agents is not permitted during the study with the following exceptions: (1) intrathecal (IT) therapy for subjects with controlled CNS leukemia at the discretion of the PI and with the agreement of the Sponsor. (2) Use of hydroxyurea for subjects with rapidly proliferative disease is allowed before the start of study therapy and for the first 2 cycles on therapy. These medications will be recorded in the case-report form.

10. Women of childbearing potential must agree to use an adequate method of contraception during the study and until 3 months after the last treatment. Males must be surgically or biologically sterile or agree to use an adequate method of contraception during the study until 3 months after the last treatment.

Adequate methods of contraception include:

- Total abstinence when this is in line with the preferred and usual lifestyle of the subject. Periodic abstinence (e.g., calendar, ovulation, symptothermal, post-ovulation methods) and withdrawal are not acceptable methods of contraception.
- Female sterilization (have had surgical bilateral oophorectomy with or without hysterectomy) or tubal ligation at least six weeks before taking study treatment. In case of oophorectomy alone, only when the reproductive status of the woman has been confirmed by follow up hormone level assessment
- Male sterilization (at least 6 months prior to screening). For female subjects on the study, the vasectomized male partner should be the sole partner for that subject
- Combination of any of the two following (a+b or a+c or b+c)

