### 7.2.2 Use of Blood Products

During the administration of IACS, subjects may receive red blood cell (RBC) or platelet transfusions, if clinically indicated, per institutional guidelines.

Myelosuppression is expected in subjects with AML due to underlying disease. Most subjects will have neutropenia, thrombocytopenia, or both at study entry. Significant or life-threatening myelosuppression may be managed with growth factor support including G-CSF, GM-CSF and platelet growth factors and erythropoietin/darbopoietin/blood transfusion according to institutional standard of care, American Society of Clinical Oncology (ASCO) Practice Guidelines, and/or NCCN Practice Guidelines.

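### The hematologic improvement criteria can be met through transfusion, growth factors or hydroxyurea, so the planned HI proportions can be biased upward by an unknown amount

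*Combined protocol and SAP*

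**What the plan says.** Section 4.4.2 sets four HI components. The erythroid criterion, for a pretreatment Hgb below 11 g/dL, is "Hgb increase by ≥1.5 g/dL". The platelet criterion is a rise in count from a pretreatment value below 100 x 10^9/L. The neutrophil criterion, for a pretreatment ANC below 1.0 x 10^9/L, is "At least 100% increase and an absolute increase" above 0.5 x 10^9/L. Blast response is a 50% or greater "reduction in peripheral blood or bone marrow blasts but still >5"%.

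Section 4.4.1 uses the Full Analysis Set for efficacy and closes its list of planned proportions with "hematologic improvements, Recurrence of Disease (RD) and Best Response measurement along with the corresponding exact 95% confidence intervals will be displayed".

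On supportive care, section 7.2.2 states that "subjects may receive red blood cell (RBC) or platelet transfusions, if clinically indicated, per institutional guidelines", and also allows myeloid and platelet growth factors and erythropoietin or darbepoetin for significant myelosuppression. Section 7.1 bars prophylactic growth factors in cycle 1 only and leaves therapeutic use open throughout. Hydroxyurea, under inclusion criterion 9 (section 5.1), "is allowed before the start of study therapy and for the first 2 cycles on therapy".

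The CR definition requires transfusion independence, given as "4 weeks without RBC transfusion and 1 week without platelet transfusion". The CRi definition waives this and says so.

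**The concern.** Each permitted agent acts on a quantity that an HI component measures. A hemoglobin or platelet value taken soon after a transfusion, a neutrophil count taken on a myeloid growth factor, or a peripheral blast count taken on hydroxyurea can cross the threshold without any effect of the study drug. HI also names no minimum duration and no assessment day, so a single value can qualify.

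The study is open label and non-randomized, so no comparison group would show how much of the HI proportion reflects supportive care. The exact interval covers sampling error only; it does not widen for misclassification. At stake is how the HI proportions are read as evidence of preliminary activity.

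**Working it through.** The plan states no target rate, threshold or sample size for HI, so there is no figure of its own to reproduce. The check is of the text, followed by an illustration of scale.

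**1. Criterion against permitted agent**

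| HI component (4.4.2) | Permitted agent acting on it (5.1, 7.1, 7.2) | Condition in the HI rule |
|---|---|---|
| Erythroid: Hgb up by 1.5 g/dL or more | RBC transfusion; erythropoietin or darbepoetin | none |
| Platelet: up by 30 x 10^9/L or more if starting above 20; otherwise from below 20 to above 20 and at least doubled | platelet transfusion; platelet growth factor | none |
| Neutrophil: at least doubled and up by more than 0.5 x 10^9/L | myeloid growth factors | none |
| Blast: down by 50% or more in blood or marrow, still above 5% | hydroxyurea in cycles 1-2, chiefly through the peripheral-blood arm | none |

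**2. Timing.** Disease assessment falls at the end of cycles 1 and 3, then every 2-3 cycles (4.4.1). The end-of-cycle-1 assessment lies inside the hydroxyurea period; the end-of-cycle-3 assessment does not. Transfusion and therapeutic growth factors are open at every assessment. Section 7.2.2 expects most subjects to enter with low neutrophils, low platelets or both, so many would plausibly be eligible for an HI component and need support.

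**3. Silence or deliberate choice.** Transfusion is addressed for CR (required absent) and for CRi (expressly waived). For HI it is neither required absent nor waived.

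**4. Scale, under assumed values.** Let t be the true HI rate and m the share of subjects without true HI who meet a threshold through support. The documents give neither.

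Apparent rate = t + (1 - t) x m.

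With t = 0 the apparent rate equals m. Expected counts are rounded to whole subjects (4.5 is taken as 4), with Clopper-Pearson 95% intervals. The sizes are 18 (expansion maximum) and 48 (enrollment maximum).

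| m (assumed) | n = 18 | n = 48 |
|---|---|---|
| 0% | 0 (0% to 18.5%) | 0 (0% to 7.4%) |
| 10% | 2 (1.4% to 34.7%) | 5 (3.5% to 22.7%) |
| 25% | 4 (6.4% to 47.6%) | 12 (13.6% to 39.6%) |
| 50% | 9 (26.0% to 74.0%) | 24 (35.2% to 64.8%) |

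With t = 10% and m = 25%, the apparent rate is 0.10 + 0.90 x 0.25 = 32.5%.

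At n = 48 and m = 25%, the interval lies wholly above the one that would be reported with no false HI. The result depends entirely on m.

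**5. The RBC window in a 21-day cycle.** In cohorts 3-7 cycle 1 lasts 21 days. A 4-week window ending on C1D21 needs 28 - 21 = 7 days before Day 1, so carrying the CR window over to HI requires a stated rule for that visit.

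**The case against.** HI is one of several descriptive proportions under a secondary, preliminary efficacy objective, with no hypothesis, threshold or stopping rule. The protocol defers analysis detail to a SAP to be finalized before database lock, and such a SAP could supply the missing conditions. Use of the agents is limited: growth factors are not prophylactic in cycle 1, and on-study hydroxyurea is confined to two cycles. Support before baseline can work the other way, because a transfused baseline Hgb makes a further 1.5 g/dL rise harder. The protocol also treats transfusion category by category, so the CR windows are not an automatic default.

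All of this stands, and it limits the weight of the point. It does not supply the missing condition: the available text contains no HI derivation rule, and the criteria followed literally score a post-transfusion rise as improvement.

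Three stronger readings are not supported:

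- A reader might infer that the share of subjects transfused approximates the share falsely scored as erythroid responders. Receiving blood is not the same as a net rise of 1.5 g/dL over pretreatment at an assessment, and the documents give no transfusion rate.
- A reader might infer that ORR is inflated. The formula under Best Response in section 4.4.2 leaves HI out. The opening sentence of 4.4.2 mentions hematologic improvements ambiguously, but the point does not depend on it.
- A reader might infer that the recommended dose would be distorted. Section 4.1.7 lists response data beside safety, PK, PD and biomarker data, and neither it nor section 4.1.10 names HI.

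**Conclusion.** The concern holds as a defect of definition. The HI criteria admit changes produced by permitted supportive care, so the planned HI proportions can be biased upward, with no control to show it. How often this would happen cannot be known from the documents; the 10%, 25% and 50% shares above are assumptions used only for scale. The effect is confined to the descriptive secondary HI proportions and their intervals. A correction before database lock is worthwhile because it is inexpensive and the plan already recognizes the issue for CR.

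**What to change.** Add these derivation rules to the SAP before database lock:

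- **Erythroid and platelet HI:** count only values that meet the transfusion-free windows already used for CR (4 weeks for RBC, 1 week for platelets). State that C1D21 assessments in 21-day cycles that cannot meet the RBC window are not evaluable for erythroid HI at that visit.
- **Growth factors:** do not count a component if an agent acting on it was given within a window fixed before database lock: erythropoietin or darbepoetin for erythroid, platelet growth factor for platelet, myeloid growth factor for neutrophil.
- **Blast response:** report marrow and peripheral blood separately, and do not count a peripheral-only response while hydroxyurea is being given.
- **Sensitivity analysis:** show HI under the section 4.4.2 definition as it stands. The blast rule in particular narrows that definition, and the SAP should say so.

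The flowcharts and section 7.2.1 already call for concomitant medications with start and end dates on the CRF. The sponsor should confirm that transfusion dates are held in the same way, including the week before Day 1. These rules do not add a minimum duration, which would be a separate choice.

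The cost is programming, lower HI rates and fewer evaluable early assessments. Some genuine improvement in subjects who were also supported will go uncounted; the sensitivity analysis shows how much rests on that.
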